### **8.3 Definitions of analysis sets**

#### **8.3.1 Efficacy analysis set**

All randomised patients with at least 1 eDiary record post-dose will be included in the efficacy analysis set. Patients will be analysed according to their randomised study drug.

#### **8.3.2 Safety analysis set**

All patients who received at least 1 single dose of randomised IP, ticagrelor or placebo, and for whom any post-dose data are available, will be included in the safety analysis set. Erroneously treated patients (e.g., those randomised to treatment A but actually given treatment B) will be accounted for in the actual treatment group.

#### **8.3.3 PK analysis set**

The PK analysis set is a subset of the safety analysis set, including all patients having at least 1 post-dose PK variable calculated.

### **8.3.4 PD analysis set**

The PD analysis set is a subset of the safety analysis set, including all patients having at least 1 post-dose PD variable calculated.

## **8.4 Outcome measures for analyses (Not Applicable)**

### **8.5 Methods for statistical analyses**

No statistical comparisons are planned for the primary objective. PRO and safety measures will be summarized descriptively using respective analysis set.

In general, all efficacy, safety, plasma concentrations of ticagrelor and active metabolite, PRU and PRO variables will be presented using descriptive statistics and graphs as appropriate. Continuous variables will be presented with descriptive statistics (n, mean, standard deviation [SD], median, min, max), within treatment group. Geometric mean and coefficient of variation (CV) will be used instead of arithmetic mean and SD, if appropriate, with CV(%) calculated as:

$$100 \cdot \sqrt{(\exp(s^2) - 1)}$$

where s is the SD of the data on a log scale.

Categorical variables will be summarized in frequency tables (number of patients and percentage), by treatment group. Data will also be presented in individual patient listings.

The presentation of pain, intensity of pain and days of analgesic use due to SCD, will be presented by week. They will also be presented by subgroup of PGIC, divided into 3 groups, improved (1 and 2), no change (3, 4 and 5) and worse (6 and 7).

In general, baseline values will be the closest observation prior to the first administration of randomised IP. For the baseline value of pain, intensity of pain and days of analgesic use, a mean value for the 4 weeks in the Screening period will be calculated.

The number of days with pain due to SCD and the analysis of analgesic use due to SCD will be analysed using an ANCOVA model, with treatment, country, baseline average value, and baseline hydroxyurea (HU) use as explanatory variables, and treatment and HU as fixed effects and centre as a random effect. Least squares differences in means between ticagrelor 45 mg and placebo and ticagrelor 10 mg and placebo with corresponding 90% confidence interval will be presented. The objectives will be analysed as a proportion of days, during the whole treatment period. A sensitivity analysis of pain and analgesic use will be performed using the ANCOVA model but excluding country and baseline HU use.

The relationship between ticagrelor dose, plasma concentration and PRU may be explored using a population PK and PK/PD modelling approach (i.e., non-linear mixed effect modelling). Data may be pooled with other appropriate ticagrelor studies for selection of doses in the planned ticagrelor SCD paediatric phase III program.

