### 2.2 Secondary objectives

Secondary Objective:	Outcome Measure :
To determine the efficacy of 2 different doses of ticagrelor versus placebo in reducing the intensity of pain due to SCD	Intensity of pain due to SCD
To assess the efficacy of 2 different doses of ticagrelor versus placebo in reducing the use of analgesics by patients with SCD	Days of analgesic use

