##### **5.1.1     **PRO****

Pain is commonly reported in clinical trials by having patients provide a rating of their own pain, i.e., it is patient reported.

The primary efficacy variable is change from baseline in number of days with pain. Secondary and exploratory variables include intensity of Worst Pain and use of analgesics. Patient reported data regarding Average Pain, Pain Right Now and Absence from school/work are exploratory variables.

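### Pain intensity versus placebo is the first secondary objective, but the ANCOVA with 90% confidence intervals covers only pain days and analgesic use

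*Protocol*

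**What the plan says.** Protocol section 2.2 has two secondary objectives in the same comparative form. The first is "To determine the efficacy of 2 different doses of ticagrelor versus placebo in reducing the intensity of pain due to SCD". The second is "To assess the efficacy of 2 different doses of ticagrelor versus placebo in reducing the use of analgesics by patients with SCD". The synopsis lists the same pair. Section 5.1.1 identifies the intensity variable: "Secondary and exploratory variables include intensity of Worst Pain and use of analgesics"; average pain and current pain are exploratory there.

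Section 8.5 (Methods for statistical analyses) then says four things that bear on intensity:

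- As a general rule, "PRO and safety measures will be summarized descriptively using respective analysis set". Continuous variables get n, mean, SD, median, minimum and maximum within each treatment group.
- "The presentation of pain, intensity of pain and days of analgesic use due to SCD, will be presented by week". The same variables are also shown by PGIC category, collapsed to three groups.
- A baseline is fixed for intensity along with the other two outcomes: "For the baseline value of pain, intensity of pain and days of analgesic use, a mean value for the 4 weeks in the Screening period" is the definition given.
- The modelling sentence is narrower and leaves intensity out: "The number of days with pain due to SCD and the analysis of analgesic use due to SCD will be analysed using an ANCOVA model". This model yields the least squares differences of each dose from placebo with 90% confidence intervals. The outcomes are expressed as proportions of days over the whole treatment period. The sensitivity version of the model names only pain and analgesic use.

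The synopsis assigns the ANCOVA to the same two outcomes.

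**The concern.** Three efficacy outcomes are primary or secondary: days with pain, pain intensity and days of analgesic use. All three are stated as comparisons with placebo. Two receive a modelled difference with an interval, and the one listed first among the secondaries does not. Followed as written, the protocol produces no planned dose-versus-placebo estimate for that objective.

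The omission matters because intensity carries information that the primary outcome cannot. Under 5.1.1.1, any NRS report from 1 to 10 makes a day with pain, and only a 0 makes it pain-free. A fall in intensity that stays above 0 therefore leaves the primary outcome unchanged. If the drug eases pain without abolishing it, intensity is where that would show, and the plan provides no adjusted contrast for it.

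**Working it through.** **1. Objectives against analyses (protocol 2.1, 2.2, 8.5, synopsis).**

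| Outcome | Stated versus placebo | Baseline mean defined | ANCOVA, LS difference, 90% CI | Descriptive by week and PGIC group |
|---|---|---|---|---|
| Days with pain (primary) | yes | yes | yes | yes |
| Pain intensity (first secondary) | yes | yes | no | yes |
| Days of analgesic use (second secondary) | yes | yes | yes | yes |

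The general sentence on descriptive summaries does not prove the gap, because pain days and analgesic days are patient-reported too and are modelled all the same. The proof is the ANCOVA sentence, which names two of the three outcomes.

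**2. Can intensity be read into the ANCOVA?** No. The model is set on a proportion-of-days scale, and a 0-10 score is not a proportion of days. In the sensitivity analysis, pain means days with pain, because it reuses that model.

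**3. Do the planned displays give a contrast?** Weekly and overall arm summaries allow a crude subtraction, with no adjustment for baseline and no planned interval. The PGIC display gives none that randomisation protects: PGIC is rated at end of treatment (5.1.1.4), so its groups form after randomisation.

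**4. What the primary misses.** Take a patient who reports 8 every day in the 28-day run-in and 2 every day for 84 days of treatment (an illustration). Proportion of days with pain: 28/28 = 1, then 84/84 = 1, so the change is 0. Mean NRS: 8, then 2, so the change is -6.

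**5. The plan's own precision figure (8.2).** Inputs: 30 per group, SD about 0.4, 90% interval, difference 0.17. The half-width for a difference of two means is 1.645 × 0.4 × √(2/30) = 1.645 × 0.4 × 0.2582 = 0.170. The stated 0.17 reproduces as the half-width of the interval. In SD units it is 0.17/0.4 = 0.425.

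**6. Precision of the missing analysis.** With the same 30 per arm, the unadjusted half-width for intensity is 1.645 × √(2/30) = 0.425 SD (0.429 SD using t with 87 degrees of freedom). The protocol gives no SD for intensity, so the values below are assumptions.

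- SD 1.5 NRS points: 0.425 × 1.5 = 0.64 points.
- SD 3.0 NRS points: 0.425 × 3.0 = 1.27 points.
- Baseline adjustment multiplies the half-width by √(1 − ρ²). At ρ = 0.5 it is 0.425 × 0.866 = 0.37 SD; at ρ = 0.7 it is 0.425 × 0.714 = 0.30 SD.

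**7. What a mean daily score measures.** With pain-free days entered as 0, mean daily NRS = (proportion of days with pain) × (mean NRS on those days). If the mean on pain days stays at m and the proportion falls by 0.17, the daily mean falls by 0.17 × m, which is 0.17 points at m = 1 and 1.7 points at m = 10. The measure combines frequency and intensity and should be labelled so.

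**The case against.** The strongest reply is that section 8.1 promises a comprehensive SAP, which is not at hand and may model intensity; nothing in 8.5 forbids it, and defining a baseline mean suggests some use was intended. That limits what can be said about the final analysis. It does not remove the mismatch in the protocol, which is not silent: it says how intensity will be presented and names the outcomes to be modelled.

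A second reply is that the study is estimation-only. Section 8.5 plans no statistical comparisons even for the primary objective, and in a phase IIb study with 30 per arm, leaving one secondary outcome descriptive may be deliberate. It is right that no hypothesis test is missing. But the primary still gets an adjusted difference and an interval, and that is all that is asked here. If description was intended, the comparative wording of the objective is what does not fit.

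A third reply is that extending the model is not purely mechanical, because a summary measure has to be chosen first. That stands, and the fix names one.

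Two stronger readings are tempting. A reader might infer that the trial cannot address intensity at all. The documents do not support this: arm means and SDs are planned, so a crude contrast can be formed, and the daily scores are collected. A reader might also try to size the problem by the share of patients with pain on nearly every day. Section 8.2 gives only a mean of 0.56 and an approximate SD of 0.4. Any such share depends on an assumed distribution, moves strongly with that SD, and describes a possible ceiling in the primary outcome and not this gap.

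**Conclusion.** The point holds as a mismatch between objective and analysis. The first secondary objective is comparative, but section 8.5 and the synopsis plan no baseline-adjusted difference and no interval for it, while giving both to the other secondary objective and to the primary. No stated number in the protocol is wrong because of this.

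The loss is one adjusted contrast per dose. Its unadjusted 90% half-width would be about 0.42 SD, which is 0.64 to 1.27 NRS points if the SD lies between 1.5 and 3.0. Baseline adjustment would bring it to 0.37 to 0.30 SD if the baseline correlation lies between 0.5 and 0.7. Those SDs and correlations are assumptions. The mismatch itself rests only on the text, and the SAP could still repair it in practice. It is worth correcting, but it does not threaten the trial's validity.

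**What to change.** In section 8.5 and the synopsis, add an ANCOVA of mean daily worst-pain NRS over the treatment period, on its own 0-10 scale. Use the baseline mean worst-pain NRS from the four screening weeks as covariate and the other terms as for the primary. The synopsis and 8.5 currently list different terms, so refer to one agreed model. Report both dose-minus-placebo least squares differences with 90% confidence intervals, and state that they are estimates and not tests. State that pain-free days count as 0, so that the measure reflects frequency and intensity together. Keep the weekly and PGIC displays as description.

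If the sponsor prefers to leave intensity descriptive, rewording the objective in 2.2 and the synopsis would also remove the mismatch, but it would give up the estimate.

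The cost is a few lines of text and one further analysis of scores the diary already collects daily. No patients, visits or assessments are added.

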## **9. STUDY AND DATA MANAGEMENT BY ASTRAZENECA**

### **9.1 Training of study site personnel**

Before the first patient is entered into the study, an AZ or its representative will review and discuss the requirements of the Clinical Study Protocol and related documents with the investigator site staff and also train them in any study specific procedures and the WBDC and ePROs system(s) utilised.

The PI will ensure that appropriate training relevant to the study is given to all of these staff, and that any new information relevant to the performance of this study is forwarded to the staff involved.

The PI will maintain a record of all individuals involved in the study (medical, nursing and other staff).

### **9.2 Monitoring of the study**

During the study, an AZ or its representative will have regular contacts with the study site, including visits to:

- Provide information and support to the Investigator(s)
- Confirm that facilities remain acceptable
- Confirm that the investigational team is adhering to the protocol, that data are being accurately and timely recorded in the eCRFs, that biological samples are handled in accordance with the Laboratory Manual and that study drug accountability checks are being performed
- Perform source data verification (a comparison of the data in the eCRFs with the patient's medical records at the hospital or practice, and other records relevant to the study) including verification of informed consent of participating patients. This will require direct access to all original records for each patient (e.g., clinic charts)
- Ensure withdrawal of informed consent to the use of the patient's biological samples is reported and biological samples are identified and disposed of/destroyed accordingly, and the action is documented, and reported to the patient

The AZ or its representative will be available between visits if the Investigator(s) or other staff members at the centre need information and advice about the study conduct.

#### **9.2.1 Source data**

Refer to the Clinical Study Agreement (CSA) for location of source data.

### **9.2.2 Study agreements**

The PI at each/the centre should comply with all the terms, conditions, and obligations of the CSA, or equivalent, for this study. In the event of any inconsistency between this Clinical Study Protocol and the CSA, the terms of Clinical Study Protocol shall prevail with respect to the conduct of the study and the treatment of patients and in all other respects, not relating to study conduct or treatment of patients, the terms of the CSA shall prevail.

Agreements between AZ delegate and the PI should be in place before any study-related procedures can take place, or patients are enrolled.

### **9.2.3 Archiving of study documents**

The Investigator follows the principles outlined in the CSA.

## **9.3 Study timetable and end of study**

The end of the study is defined as ‘the last visit of the last patient undergoing the study’.

The study is expected to start in Q2 2015 and to end by Q3 2016.

The Sponsor will notify the PI(s) when recruitment is complete.

The study may be terminated at individual centres if the study procedures are not being performed according to GCP and local regulations, or if recruitment is slow. AZ may also terminate the entire study prematurely if concerns for safety arise within this study or in any other study with ticagrelor.

## **9.4 Data management by AstraZeneca or delegate**

Data management will be performed by the AZ delegate.

Data will be entered into the WBDC system at the study site. Trained site staff will be entering the data as specified in the protocol and according to the eCRF instructions. Data entered into the WBDC system will be immediately saved to a central database and changes tracked to provide an audit trail. The data will then be Source Data Verified, reviewed, queried and updated as needed.

AEs and medical/surgical history will be classified according to the terminology of the latest version the Medical Dictionary for Regulatory Activities (MedDRA). Medications will be classified according to the AZ Drug Dictionary. All coding will be performed by the AZ delegate.

The PI is responsible for signing the eCRF and this may be delegated to a trained Investigator.

The data will be validated as defined in the Data Management Plan. Quality control procedures will be applied to each stage of data handling to ensure that all data are reliable and have been processed correctly. The Data Management Plan will also clarify the roles and

responsibilities of the various functions and personnel involved in the data management process.

When all data have been coded, validated, signed and locked, clean file will be declared. Any treatment revealing data may thereafter be added and the final database will be locked. A copy of the eCRF will be archived at the study site when the study is completed.

### **Serious Adverse Event (SAE) Reconciliation**

SAE reconciliation reports are produced and reconciled with the Patient Safety database and/or the investigational site.

### **Data associated with human biological samples**

Data associated with biological samples will be transferred from laboratory(ies) internal or external to AZ.

### **Management of external data**

Data Management determines the format of the data to be received from external vendors and coordinates the flow of data to the clinical database. Data Management will assure that the data collection tools for eDiary and IVRS are tested and validated. External data reconciliation will be done with the clinical database as defined in the Data Management Plan.

## **10. ETHICAL AND REGULATORY REQUIREMENTS**

### **10.1 Ethical conduct of the study**

The study will be performed in accordance with ethical principles that have their origin in the Declaration of Helsinki and are consistent with International Conference on Harmonisation (ICH)/Good Clinical Practice (GCP), applicable regulatory requirements and the AZ policy on Bioethics and Human Biological Samples.

### **10.2 Patient data protection**

The ICF will incorporate (or, in some cases, be accompanied by a separate document incorporating) wording that complies with relevant data protection and privacy legislation.

### **10.3 Ethics and regulatory review**

An Ethics Committee (EC)/ Institutional Review Board (IRB) should approve the final study protocol, including the final version of the ICF and any other written information and/or materials to be provided to the patients. The Investigator will ensure the distribution of these documents to the applicable EC/IRB, and to the study site staff.

The opinion of the EC/IRB should be given in writing. The Investigator should submit the written approval to AZ or its representatives before enrolment of any patient into the study.

The EC/IRB should approve all advertising used to recruit patients for the study.

AZ should approve any modifications to the ICF that are needed to meet local requirements.

If required by local regulations, the protocol should be re-approved by the EC/IRB annually.

Before enrolment of any patient into the study, the final study protocol, including the final version of the ICF, is approved by the national regulatory authority or a notification to the national regulatory authority is done, according to local regulations.

AZ will handle the distribution of any of these documents to the national regulatory authorities.

AZ will provide Regulatory Authorities, EC/IRB and PIs with safety updates/reports according to local requirements.

Each PI is responsible for providing the EC/IRB with reports of any serious and unexpected adverse drug reactions from any other study conducted with the investigational product. AZ or its representatives will provide this information to the PI so that he/she can meet these reporting requirements.

#### **10.4 Informed consent**

This study consists of 2 ICFs, the main ICF that allows patient to participate in the main study and the other optional ICF that allows subjects to participate in optional biomarker research. The subject may participate in the main study without participating in the optional component. To participate in the optional component of the study the subject must sign and date both the consent forms for the main study and the optional component of the study. Enrolment code must be obtained from IVRS/IWRS. The principal investigator(s) is responsible for ensuring that consent is given freely and that the subject understands that they may freely discontinue the optional biomarker aspect of the study at any time.

The PI(s) at each centre will:

- Ensure each patient is given full and adequate oral and written information about the nature, purpose, possible risk and benefit of the study
- Ensure each patient is notified that they are free to discontinue from the study at any time
- Ensure that each patient is given the opportunity to ask questions and allowed time to consider the information provided
- Ensure each patient provides signed and dated informed consent before conducting any procedure specifically for the study
- Ensure the original, signed ICF(s) is/are stored in the Investigator's Study File

- Ensure a copy of the signed ICF is given to the patient
- Ensure that any incentives for patients who participate in the study as well as any provisions for patients harmed as a consequence of study participation are described in the ICF that is approved by an EC/IRB.

## **10.5 Changes to the protocol and informed consent form**

Study procedures will not be changed without the mutual agreement of the PI and AZ or AZ delegate.

If there are any substantial changes to the study protocol, then these changes will be documented in a study protocol amendment and where required in a new version of the study protocol (Revised Clinical Study Protocol).

The amendment is to be approved by the relevant EC/IRB and if applicable, also the national regulatory authority approval, before implementation. Local requirements are to be followed for revised protocols.

AZ or AZ delegate will distribute any subsequent amendments and new versions of the protocol to each PI(s). For distribution to EC/IRB see Section [10.3](#).

If a protocol amendment requires a change to a centre's ICF, AZ or AZ delegate and the centre's EC/IRB are to approve the revised ICF before the revised form is used.

If local regulations require, any administrative change will be communicated to or approved by each EC/IRB.

## **10.6 Audits and inspections**

Authorised representatives of AZ, a regulatory authority, or an EC may perform audits or inspections at the centre, including source data verification. The purpose of an audit or inspection is to systematically and independently examine all study-related activities and documents, to determine whether these activities were conducted, and data were recorded, analysed, and accurately reported according to the protocol, GCP, guidelines of the ICH, and any applicable regulatory requirements. The Investigator will contact AZ or AZ delegate immediately if contacted by a regulatory agency about an inspection at the centre.

